#### **7.5 Baseline assessments (Visit 2, 1 to 28 days after screening):**

The methods of the assessments are described in detail in section 7.9.

- I. Vital Signs (see Appendix B and section 7.9.2 for details of the tests that will be used). Vital signs will be continuously monitored throughout the infusion until the participant has recovered. This monitoring will be recorded on a standard observation chart, stored as source data. The eCRF will record 3 sets of readings, one prior to the infusion, another after the infusion terminates, and then finally after the participants recovery.
- II. Bloods, blood samples for BDNF and ketamine will be obtained pre-IMP/placebo administration and post IMP administration (see Appendix B and section 7.9.2 for details of the tests that will be used.)
- III. Full eligibility determination
- IV. Urine Drug Screen (see Appendix B and section 7.9.2 for details of the tests that will be used.)
- V. Pregnancy test in WOCBP (urine test)
- VI. Breathalyser
- VII. Randomisation
- VIII. IMP/placebo Administration (see section 7.6)
- IX. SCRAM-X checks (if already fitted) / alternative SCRAM-X fitting (where routine fitting at screening not completed)
- X. Relapse Prevention Based Cognitive Behavioural Therapy
- XI. Adverse Events Review

- XII. Concomitant medication review
- XIII. BDI
- XIV. HAM-D
- XV. POMS
- XVI. STAI
- XVII. ACQ-NOW
- XVIII. BPRS
- XIX. PSI
- XX. Alcohol Timeline Follow Back
- XXI. Fagerstrom Nicotine Dependence
- XXII. Craving VAS
- XXIII. SF-12
- XXIV. Prose Recall
- XXV. Delay Discounting (monetary choice questionnaire)
- XXVI. Stop Signal Reaction time
- XXVII. Working memory (digit span WAIS-IV)
- XXVIII. Adverse Effect VAS( e.g. nausea, intoxication, anxiety, memory : 20 mins before infusion and every 20 mins for next 2 hours)
- XXIX. Pattern Recognition Memory Test

**7.6 Treatment procedures (visits 2 (i.e. baseline; 1 to 28 days after screening), visit 4 (4 to 21 days after visit 2) and 6 (4 to 21 days after visit 4))**

IMP Dosing Patients will receive 3 x weekly infusions of ketamine (Ketalar®) (0.8mg/kg made up to 50ml with saline over 40 minutes) or 3 x weekly infusion of placebo (0.9% saline over 40 minutes). The drug/placebo will be prepared in a blinded fashion by pharmacy (who are unblinded) or delegated unblinded site staff on the ward at site and will be administered by the research anaesthetist at the Clinical Research Facility at sites who will remain blinded.

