- The Alcohol TimeLine Follow Back (TLFB) is a drinking assessment method that obtains estimates of daily drinking and has been evaluated with clinical and nonclinical populations. Using a calendar, people provide retrospective estimates of their daily drinking over a specified time period. Several memory aids can be used to enhance recall (e.g., calendar; key dates serve as anchors for reporting drinking; standard drink conversion). The Alcohol TLFB has been shown to have good psychometric characteristics with a variety of drinker groups, and can generate variables that provide a wide range of information about an individual's drinking (e.g., pattern, variability, and magnitude of drinking).
- A drink diary will be given to each participant to take home in between Visits 8, 9 and 10. Participants will be asked to record their alcohol consumption every day in between study visits. Drink diaries are regularly used in alcohol research to record subjective alcohol consumption.
- Alcohol Craving Questionnaire - short-form (ACQ-NOW) is a 12-item scale that assesses current alcohol craving.

Validated Neurocognitive measures:

- Delay discounting (e.g. monetary choice questionnaire): this is a task that measures an individual's preference for immediate small award over a long term bigger gain.
- Prose recall task: this looks at episodic memory by testing participants recall of a short news broadcast.

- Stop signal task: Stop signal reaction time examines response inhibition, participants have to inhibit prepotent responses to stimuli on the screen when they see a cue or 'stop signal'.
- Working memory task (e.g. digit span WAIS-IV): Working memory measures an individual's ability to maintain and manipulate small amounts of information.
- Pattern recognition memory task (BPS-O Task) is a memory task that taps hippocampal functioning and requires participants to distinguish between perceptually similar items that they have seen before and those they have not.

Questionnaires that are not validated:

- The Pre-Screening questionnaire has been developed to assess suitability for inclusion into the trial.
- Adverse Effects Visual Analogue Scale (VAS) has been developed to measure adverse events during the ketamine infusion and treatment.
- Craving VAS: a one item visual analogue scale will be used to assess craving for alcohol anchored at one end with 'No desire to drink alcohol' and the other 'Very strong desire to drink alcohol'.

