Breathalyser tests will be used at each visit for the following reasons:

- Screening & re-screening – To assess eligibility
- Baseline visit (1st infusion) – To assess eligibility/ensure safety of IMP administration/ensure patient is able to complete cognitive tasks and questionnaires, as well as engage with therapy/education
- Visit 3, 5, 7 & 8 – To ensure patient is able to complete cognitive tasks and questionnaires, as well as engage with therapy/education
- Visit 4 & 6 (2nd & 3rd infusion) – To ensure safety of IMP administration/ensure patient is able to complete cognitive tasks and questionnaires, as well as engage with therapy/education
- Visit 9 & 10 - To ensure patient is able to complete cognitive tasks and questionnaires

Once randomised, if a patient attends for any visit and does not blow 0 on the breathalyser the visit will be terminated (either for the primary purpose of safety on infusion visits or of data integrity on non-infusion visits) and the patient invited to re-attend to complete the visit within the allocated visit window.

Concomitant Medication: All prescription medication, over-the-counter medication, vitamins, and/or herbal supplements will be recorded on case report forms (CRFs).

Vital Signs: Resting pulse, pulse oximetry and blood pressure (BP) measurements will be measured at each visit phase for safety monitoring. Vital signs will be continuously monitored throughout the infusion until the participant has recovered. This monitoring will be recorded on a standard

observation chart, stored as source data. The eCRF will record 3 sets of readings, one prior to the infusion, another after the infusion terminates, and then finally after the participants recovery.

Physical Examination: Height, weight and oral/tympanic temperature will be recorded.

At screening a physician will perform a physical examination of the cardiovascular, respiratory, GI and neurological system to a level of detail that would be expected for a patient due to receive anaesthesia.

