### **13.3.3 Secondary outcome analysis**

There are 15 secondary outcomes (section 13.1.2); all of these outcomes will be reported descriptively on an ITT complete case basis; additionally, the between-group mean differences and 95% confidence intervals will be reported on an exploratory basis for the primary comparison (all ketamine participants versus all non-ketamine participants). Also, as a feasibility outcome, attrition will be reported as a proportion (with 95% confidence interval) overall and by arm.

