4.5 Purpose of the analyses

The purposes of the analyses are as follows:

- (i) to provide baseline descriptive data by trial arm;
- (ii) to assess the feasibility of data collection;
- (iii) to assess loss to follow-up at 3 and 6 months;

- (iv) to assess the proportion of missing data at 6 months;
- (v) to provide descriptive outcome data by trial arm (ketamine vs placebo, psychotherapy vs psychoeducation, and all four arms individually) at 6 months;
- (vi) to provide relative risks (with 95% confidence intervals) for relapse of alcohol consumption comparing (a) ketamine vs placebo; (b) ketamine plus psychotherapy vs ketamine plus psychoeducation; (c) ketamine plus psychotherapy vs placebo plus psychoeducation;
- (vii) to provide mean difference (with 95% confidence intervals) for percentage of days abstinent at 6-month follow-up for the same combinations by arm as for (vi); and
- (viii) to descriptively report adverse events.

All inferential analyses are to be regarded as exploratory and viewed with caution due to lack of statistical power and multiple testing. For the primary outcomes, the primary analyses will be performed on an intention to treat (ITT) basis using complete case data only (see Section 6.5 for approaches to missing primary outcome data). As a sensitivity analysis, the inferential analyses for the primary outcomes only (vi and vii above) will be performed using only those participants deemed to have completed their allocated interventions to a specified degree (per protocol analysis). For the participants who receive ketamine, a per protocol treatment will be defined as receiving three or more infusions. No specification of a minimum treatment has been defined for psychotherapy/psychoeducation. Hence, all participants who receive placebo drug therapy will be considered as having been treated per protocol. For the secondary outcomes, only an ITT analysis using complete case data will be performed. All analyses will be performed by a statistician who is blinded to treatment allocation. All analyses will be performed using Stata v14.

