Response inhibition (Stop Signal Reaction time)	Continuous	6 months	Computer task: participant completed
Working memory	Continuous	6 months	Questionnaire: participant report
Hippocampal functioning (Pattern Recognition Test)	Continuous	6 months	Computer task: participant completed
Adverse effects (visual analogue scale)	Continuous	6 months	Questionnaire: participant report

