Table 5 Relapse of alcohol use and percentage of days abstinent at 6-month follow-up: per protocol^a population using complete case data.

Outcome	Ketamine (n=)	Placebo (n=)	PT (n=)	PE (n=)	Ketamine + PT (n)	Ketamine + PE (n)	Placebo + PT (n)	Placebo + PE (n)	Ketamine vs placebo RR (95% CI)	Ketamine + PT vs Ketamine + PE RR (95% CI)	Ketamine + PT vs placebo +PE RR (95% CI)
Relapse; n (%) Timeline follow back											
									Ketamine vs placebo mean difference (95% CI)	Ketamine + PT vs Ketamine + PE mean difference (95% CI)	Ketamine + PT vs placebo +PE mean difference (95% CI)
Percentage days abstinent; mean (SD); median [IQR] Timeline follow back											

^aPer protocol population defined as receiving at least three ketamine infusions. No definition of per protocol for placebo, psychotherapy, or psychoeducation interventions.

PE: Psychoeducation

PT: Psychotherapy

Table 6 Relapse of alcohol use and percentage of days abstinent at 6-month follow-up: intention to treat population using complete case and imputed data.

Outcome	Ketamine (n=)	Placebo (n=)	PT (n=)	PE (n=)	Ketamine + PT (n)	Ketamine + PE (n)	Placebo + PT (n)	Placebo + PE (n)	Ketamine vs placebo RR (95% CI)	Ketamine + PT vs Ketamine + PE RR (95% CI)	Ketamine + PT vs placebo +PE RR (95% CI)
Relapse; n (%) Timeline follow back											
									Ketamine vs placebo mean difference (95% CI)	Ketamine + PT vs Ketamine + PE mean difference (95% CI)	Ketamine + PT vs placebo +PE mean difference (95% CI)
Percentage days abstinent; mean (SD); median [IQR] Timeline follow back											

PE: Psychoeducation

PT: Psychotherapy

Table 7 Secondary outcomes at 3-month follow-up

Outcome	Ketamine (n=)	Placebo (n=)	PT (n=)	PE (n=)	Ketamine + PT (n)	Ketamine + PE (n)	Placebo + PT (n)	Placebo + PE (n)	Ketamine vs placebo mean difference (95% CI)
Number of continuous days abstinent ^{a,b} ; mean (SD), median [IQR]									
Percentage days abstinent ^{a,b} ; mean (SD); median [IQR]									

PE: Psychoeducation

PT: Psychotherapy

^aAbstinent means not using alcohol at all.

^bOutcomes measured using timeline follow-back.

Table 8 Secondary outcomes at 6-month follow-up

Outcome	Ketamine (n=)	Placebo (n=)	PT (n=)	PE (n=)	Ketamine + PT (n)	Ketamine + PE (n)	Placebo + PT (n)	Placebo + PE (n)	Ketamine vs placebo mean difference (95% CI)
Profile of Mood states; mean (SD), n									
Beck Depression Inventory; mean (SD)									
Hamilton Depression Scale; mean (SD), n									

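### Primary objective 2 (safety and tolerability) is only partly served: infusion-day adverse-effects ratings have no stated analysis, and the adverse event description has no named source

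*SAP*

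**What the plan says.** Protocol section 3 and SAP 5.1 make safety and tolerability of ketamine the second primary objective. The protocol Summary says tolerability is indicated by drop-out and lists adverse events beside it.

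**Adverse-effects VAS.** Protocol 7.9.1 states that the "Adverse Effects Visual Analogue Scale (VAS) has been developed to measure adverse events during the ketamine infusion and treatment". At visit 2 it is rated "20 mins before infusion and every 20 mins for next 2 hours" (7.5), and 7.7 repeats that schedule for visits 4 and 6. Appendix B also schedules it at visits 3, 5, 7, 8, 9 and 10, and 11.2 lists it for CRF entry. Protocol 13.1.2 names it as a secondary outcome without a visit. SAP Table 2 assigns the row "Adverse effects (visual analogue scale" to 6 months. Its only output shell is headed "Table 8 Secondary outcomes at 6-month follow-up", and SAP 4.5(v) undertakes "to provide descriptive outcome data by trial arm (ketamine vs placebo, psychotherapy vs psychoeducation, and all four arms individually) at 6 months".

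**Other infusion-visit data.** For vital signs, "The eCRF will record 3 sets of readings, one prior to the infusion, another after the infusion terminates", with a third set after recovery (7.9.1). BPRS and PSI are also scheduled at visits 2, 4 and 6. The SAP analyses BPRS and PSI at 6 months only and has no entry for vital signs.

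**Attrition.** SAP 4.5(iii) plans "to assess loss to follow-up at 3 and 6 months", and protocol 13.3.3 says "attrition will be reported as a proportion (with 95% confidence interval) overall and by arm".

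**Adverse events.** SAP 4.5(viii) and 6.6 promise a description by arm, and Tables 3 to 8 contain no adverse event shell. Protocol 10.2 opens by sending all adverse events to the medical records and the CRF. It then confines events listed in Appendix C or 10.3.3 to the medical notes unless they are serious. Protocol 11.2 likewise keeps expected non-serious events out of the CRF.

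**The concern.** The trial collects the data that would show how well the infusions are tolerated, but the plan does not carry them through to a result. Protocol 9.6 itself names psychotomimetic effects as a threat to tolerability and retention. Those are the effects present while the infusion-day ratings are taken, and they are also among the events that 10.2 and 11.2 keep out of the CRF.

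Two things are at stake. First, acute tolerability would have no symptom summary by arm. A 6-month rating can show persistent effects but says nothing about the infusions. It is also a complete-case analysis, so anyone who left because of side effects and misses visit 10 is absent from it. Second, an adverse event table drawn from the database would lack ketamine's known non-serious effects. These should be more frequent on ketamine than on saline, so leaving them out would make the arms look more alike than they were.

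**Working it through.** The plan states no figure that bears on this point, so the check traces the data from collection to output and then sizes the gap.

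**1. VAS ratings collected and analysed.** Protocol 7.5 and 7.7 give one pre-infusion rating and one every 20 minutes for 2 hours: 1 + 120/20 = 7 per infusion, or 8 if a rating at time zero is also counted.
- Infusion days: 3 × 7 = 21 (or 3 × 8 = 24).
- Visits 3, 5, 7, 8, 9 and 10, assuming one rating each: 6.
- Total: 27 (or 30).
- Assigned to analysis: 1, at visit 10. That is 1/27 = 3.7% (or 1/30 = 3.3%) of ratings, and 1 of 9 visits. Infusion-day ratings assigned to analysis: 0.

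**2. Time from last infusion to the analysed rating.** Visits 4 and 6 each fall 4 to 21 days after the preceding infusion visit, so visit 6 is on day 4 + 4 = 8 to 21 + 21 = 42 after visit 2. Visit 10 is at 23 to 25 weeks, day 161 to 175. The gap runs from 161 − 42 = 119 days to 175 − 8 = 167 days.

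**3. Precision available at each time.** The unadjusted 95% CI half-width for a mean difference, in SD units, is t(0.975, 2n − 2) × √(2/n).
- Visit 2, if all 48 per drug arm contribute: t(0.975, 94) × √(2/48) = 0.405.
- Six months, at the plan's 50% drop-out (24 per drug arm): t(0.975, 46) × √(2/24) = 0.581.

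These are the two ends of the range. The protocol calls 50% drop-out very conservative, and full contribution at visit 2 is the best case.

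**4. Whether attrition stands in for tolerability.** Under 9.11 a participant with intolerable side effects is withdrawn from IMP. Under 7.11.1 such a participant is still invited to visits 9 and 10. Attrition is counted as loss to follow-up at 3 and 6 months. Someone who stops the drug because of side effects and attends both visits therefore counts as retained.

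**5. Where adverse events go.**
- 10.2, opening: all events in the medical records and CRF.
- 10.2, exception: Appendix C and 10.3.3 events in the notes only, unless serious.
- 11.2: expected non-serious events not collected in the CRF.
- 11.3 and SAP 6.1: the statistician analyses the trial database. No route is described for notes-only events.

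Appendix C lists 17 Common + 9 Uncommon + 11 Rare + 3 Not known = 40 terms. The ketamine line in 10.3.3 names 8 effects. As an illustration only, applying the Common band of Appendix C (1/100 to under 1/10, from anaesthetic use) per participant gives 48 × 0.01 = 0.48 to 48 × 0.10 = 4.8 of 48 ketamine participants for each such term. If those events were non-serious, they would not reach a database-built table. Protocol 2.5 undertakes to ask about cystitis when recording adverse events, yet cystitis is in Appendix C, so a non-serious case would go to the notes only.

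**The case against.** The protocol chose its indicator: tolerability by drop-out, with adverse events beside it. Both are planned by arm. Treatment discontinuation is not invisible either. Its reason goes into the CRF (7.11.1), the per-protocol set requires three ketamine infusions (SAP 4.5), and a participant flow diagram is planned. Serious and unlisted events reach the CRF, and clinically significant laboratory abnormalities are recorded as adverse events. A reader might therefore infer too much in saying that tolerability goes unassessed, and the documents do not support that. What stands against the defence is step 4 of the working, and that no summary of discontinuation reasons is listed in SAP 4.5 or Tables 3 to 8. The flow diagram is not reproduced in the text available, so its content cannot be judged.

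The 6-month restriction can also be called loose. Table 2's column is headed as timepoints measured, SAP 5.2 gives the VAS no time, Table 8 is an example shell, and SAP 4.5(v) cannot be exhaustive because Table 7 reports 3-month outcomes. But the VAS is measured at nine visits, so the column makes sense only as the time of analysis, and no other place in the SAP gives the infusion-day ratings one.

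A reader might infer that BPRS and PSI go unanalysed. They do not: both are secondary variables at 6 months, and only their infusion-visit values lack a stated analysis. A reader might also infer that 10.2 and 11.2 define different sets of excluded events. That is strained, because 10.2 lies within section 10 and brings in Appendix C by name. The clearer conflict is between the opening of 10.2 and its own exception.

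Finally, the scale is unvalidated (7.9.1), and adding outcomes widens an already exploratory family. Both points are fair and shape the remedy.

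**Conclusion.** The point holds, and it should be fixed. Primary objective 2 is partly served, by attrition, serious adverse events and the other events that reach the CRF. It is not served for acute symptoms: none of the 21 to 24 infusion-day VAS ratings per participant has a stated analysis, and the one analysed rating comes 119 to 167 days after the third infusion. Infusion-visit vital signs, BPRS and PSI have no stated analysis either. The VAS data are not lost, since 11.2 sends them to the CRF; only the plan for them is missing.

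The adverse event limb is conditional. SAP 6.6 does not say that the table will come from the database alone, so a reader who infers certain bias goes further than the documents allow. If it does come from there, the notes-only rule removes known ketamine effects and moves the contrast toward no difference. The size of that shift cannot be derived, because the only frequencies given are from anaesthetic use. The rating counts assume one VAS rating at each non-infusion visit, and the half-widths are unadjusted for site.

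**What to change.** (a) In SAP 5.2 and Tables 2 and 8, and in 4.5(v), add one prespecified exploratory ketamine-versus-placebo summary of the infusion-day VAS. An example is peak change from the pre-infusion rating, reported for visit 2 first because it is least affected by drop-out, as a site-adjusted mean difference with 95% CI and no p-value, in line with SAP 6.3 and 6.4. State whether items are totalled or kept separate. The four items the protocol gives as examples, analysed by peak and change at three visits, would make 4 × 2 × 3 = 24 estimates, more than the existing 19 secondary variables, so a single summary is preferable. Keep the 6-month value as a check on persistent effects, and note that the scale is unvalidated. Infusion-visit vital signs, BPRS and PSI can be described without comparison. The protocol should say whether BPRS and PSI are rated before or after the infusion.

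(b) Reconcile the opening of protocol 10.2 with its exception and with 11.2. In SAP 6.6, name the adverse event source and add a shell counting participants with each event by arm and severity. Then either transcribe the notes-only events before database lock, blind to drug allocation, or state in the table which event categories are excluded.

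The cost is one or two extra exploratory tables and wording changes to both documents. If transcription is chosen, it also means note review at two sites, with less reliable retrospective grading of severity. No new assessments are needed.

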6.2 Types of analyses

The primary analyses, for both primary and secondary outcomes, will be based on the ITT population, using complete case data only. The primary outcomes will be reported descriptively using ITT data. Inferential analyses for the three two-arm comparisons (ketamine vs placebo; ketamine plus psychotherapy vs ketamine plus psychoeducation; and ketamine plus psychotherapy vs placebo plus psychoeducation) will be performed for the primary outcomes using ITT and per protocol data. The secondary outcomes will be reported descriptively by arm using ITT data, and inferential analyses will be performed using ITT data for the primary two-arm comparison only, ketamine vs placebo.

6.3 Covariates and subgroups

All inferential analyses will be adjusted by site. Due to the small number of participants, and the feasibility nature of the study, no subgroup investigations will be performed.

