***Screening Visit (Visit 1 Day 28 to 1 days before visit 2 (baseline) visit):***

Formal screening will take place at this screening visit as set out in Appendix B and listed below. The methods of the assessments are explained in section 7.9. Consent will be taken from the patient prior to the assessments at this visit (see section 7.1).

Following screening and eligibility determination, those still meeting criteria for inclusion in the study can be fitted with the SCRAM-X bracelet anytime between the screening visit and visit 2. A date for visit 2 will be arranged, within 28 days of the screening date.

The visit schedule is set out below and as a chart in Appendix B:

- I. Trial Discussion
- II. Informed Consent
- III. Medical history
- IV. Physical Examination (repeat screens of height and weight may be conducted if initial results do not fall within boundaries described in 5.2 but patient meets other criteria for eligibility)
- V. SCID
- VI. Vital Signs (repeat screens of blood pressure may be conducted if initial results do not fall within boundaries described in 5.2 but patient meets other criteria for eligibility)
- VII. Bloods to assess eligibility (U&Es, LFTs, FBC; repeat screens may be conducted every 7days if initial results do not fall within boundaries described in 5.2 but patient meets other criteria for eligibility, see Appendix B and section 7.9.2 for details of the tests that will be used).
- VIII. Eligibility Determination
- IX. Urine Drug Screen (repeat screens may be conducted if initial results do not fall within boundaries described in 5.2 but patient meets other criteria for eligibility, see Appendix B and section 7.9.2 for details of the tests that will be used)
- X. Pregnancy test in WOCBP (urine test)
- XI. Breathalyser (repeat breathalyser screens may be conducted if initial result does not fall within boundaries described in 5.1 but patient wishes to continue with detoxification and return once they are abstinent)
- XII. Routine SCRAM-X fitting (unless study team deem this not possible)
- XIII. Concomitant medication review
- XIV. Alcohol and Drug Use History
- XV. BDI
- XVI. HAM-D
- XVII. Columbia Suicide Severity Rating Scale
- XVIII. Reasons for drinking questionnaire
- XIX. STAI
- XX. ACQ-NOW

- XXI. BPRS
- XXII. PSI
- XXIII. Alcohol Timeline Follow Back

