## **13.3 Statistical analysis plan**

### **13.3.1 Summary of baseline data and flow of patients**

We will assess the comparability of the randomised groups including each factor including demographics and the baseline assessments described in section 7. We plan to produce a consort flow diagram (<http://www.consort-statement.org/>).

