5.2 Endpoints

The primary and secondary outcome variables are set out in the Protocol, Final Version 12, 20.01.2020, Section 13.1 (reproduced in Table 2). There are two primary outcomes:

- 1) relapse (defined as 5 drinks (8.1 units alcohol) in men and 4 drinks (6.5 units alcohol) in women on a single occasion) at 6-month follow-up; binary outcome; and
- 2) percentage days abstinent (not using alcohol at all) at 6-month follow-up; percentage, to be analysed as a continuous variable.

The two primary outcomes are to be derived from timeline follow-back.

There are 19 secondary variables, derived from 16 secondary outcomes (Protocol, Final Version 12, 20.01.2020, Section 13.1.2; depression is measured by two variables, Beck Depression Inventory and Hamilton Depression Scale; Short Form Health Survey 12 (SF-12) produces a physical and a mental component scale; psychotic symptoms is measured by two variables, Brief Psychiatric Rating Scale and Psychotomimetic States Inventory).

- 1) maximum number of days of continuous abstinence within the first 3 months (time-line follow back); continuous;
- 2) percentage days abstinent at 3 months (time-line follow back); percentage, to be analysed as a continuous outcome;
- 3) Profile of Mood states; continuous;
- 4) Beck Depression Inventory; continuous;
- 5) Hamilton Depression Scale; continuous;
- 6) Speilberger Trait Anxiety Inventory; continuous;
- 7) Brief Psychiatric Rating Scale; continuous;
- 8) Psychotomimetic States Inventory; continuous;
- 9) Fagerstrom Test of Nicotine Dependence (FTND; smokers only); continuous;
- 10) Alcohol craving (visual analogue scale); continuous;
- 11) Alcohol Craving Questionnaire - short-form (ACQ-NOW);
- 12) Short Form Health Survey 12 (SF-12), physical component scale (PCS); continuous;
- 13) Short Form Health Survey 12 (SF-12), mental component scale (MCS); continuous;
- 14) episodic memory (Prose Recall); continuous;
- 15) delay discounting; continuous;
- 16) response inhibition (Stop Signal Reaction time); continuous;
- 17) working memory; continuous;
- 18) hippocampal functioning (Pattern Recognition Test); continuous; and
- 19) adverse effects (visual analogue scale); continuous.

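### Inferential analyses adjust for site only, although baseline values are scheduled for 17 of the 19 secondary variables; the estimates are valid but may be less precise than they could be

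*SAP*

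**What the plan says.** - **Covariates.** SAP 6.3: "All inferential analyses will be adjusted by site". The section rules out subgroups because the trial is small, but gives no reason for omitting other covariates. None is named elsewhere in the SAP or in Protocol 13.3.
- **Inferential output.** For secondary outcomes, SAP 6.2 states that "inferential analyses will be performed using ITT data for the primary two-arm comparison only, ketamine vs placebo". SAP 6.4 limits reporting to point estimates with 95% confidence intervals and no p-values. SAP Tables 7 and 8 show a plain mean difference for each variable.
- **Outcomes.** SAP 5.2: "There are 19 secondary variables, derived from 16 secondary outcomes". Two of them are 3-month abstinence variables: the "maximum number of days of continuous abstinence within the first 3 months", and percentage days abstinent.
- **Baseline data.** Protocol 7.5 and Appendix B schedule the other 17 variables at visit 2, and Protocol 7.7 repeats them at visit 10. Timeline follow-back is scheduled at screening (Protocol 7.4) and at visit 2. The "Alcohol and Drug Use History" is also taken at screening.
- **Stated use of baseline data.** Protocol 13.3.1: "We will assess the comparability of the randomised groups including each factor including demographics and the baseline assessments described in section 7". SAP 4.5 adds only a baseline description by arm.
- **Timing within visit 2.** Among the outcome measures, Protocol 7.5 fixes a pre-infusion time only for the adverse effects scale: "20 mins before infusion and every 20 mins for next 2 hours".

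**The concern.** The plan compares 6-month scores between arms and ignores each participant's own starting score. Where starting and later scores are correlated, a model that includes the starting score leaves less unexplained variation and gives a narrower interval for the same participants. Interval estimates are this trial's only inferential product, and the planning case leaves 24 per drug arm. Any precision given up is therefore given up in the result itself. The values that could recover some of it are already on the visit schedule.

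**Working it through.** **1. The plan's own precision figures.** These concern relapse only; the documents give none for a continuous outcome.
- Protocol 13.2.1, 50% versus 25% with 24 per drug arm: SE = √(0.5×0.5/24 + 0.25×0.75/24) = 0.135. The 90% interval is 0.25 ± 1.645×0.135, or 2.8% to 47.2%. This reproduces the stated 3% to 47%.
- SAP 4.6, 95% interval width of 37 points: the exact interval for 6/24 is 9.8% to 46.7%, width 36.9. This also reproduces. It is the interval for the ketamine rate alone, not for the difference.

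**2. Count of variables.** 19 − 2 abstinence variables = 17 scheduled at visit 2: POMS, BDI, HAM-D, STAI, BPRS, PSI, FTND, craving scale, ACQ-NOW, SF-12 physical, SF-12 mental, prose recall, delay discounting, stop signal, digit span, pattern recognition and adverse effects scale.

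**3. Gain from adding the baseline value.** Let r be the correlation between baseline and outcome. It is not in the documents, so 0.3, 0.5 and 0.7 are assumed.
- Width before adjustment, 24 versus 24: 2 × t × √(2/24) = 2 × 0.581 = 1.16 SD.
- Adjustment multiplies the residual SD by √(1 − r²) = 0.954, 0.866 or 0.714.
- Against this stand one lost degree of freedom and chance correlation between arm and baseline. Simulation of arm + site versus arm + site + baseline (5,000 runs per setting, equal site split assumed) puts this cost at a width factor of 1.011 for 24 versus 24, read off at r = 0.
- Combined for 24 versus 24: 1.011 × 0.954 = 0.96, 1.011 × 0.866 = 0.88 and 1.011 × 0.714 = 0.72. The directly simulated ratios are 0.966, 0.876 and 0.723.

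Simulated 95% interval widths in SD units, with the ratio to site-only in brackets:

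| Analysed | Site only | r = 0.3 | r = 0.5 | r = 0.7 | Break-even r |
|---|---|---|---|---|---|
| 12 vs 12 | 1.68 | 1.64 (0.98) | 1.50 (0.89) | 1.23 (0.73) | 0.2 to 0.25 |
| 24 vs 24 | 1.16 | 1.12 (0.97) | 1.01 (0.88) | 0.83 (0.72) | about 0.15 |
| 48 vs 48 | 0.81 | 0.78 (0.96) | 0.70 (0.87) | 0.58 (0.72) | about 0.1 |

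The 12 versus 12 row applies to the two single-cell comparisons of percentage days abstinent after 50% dropout. The 48 versus 48 row is the case of no dropout.

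**4. In participants.** At 24 versus 24, r = 0.5 gives the precision of 48/0.876² ≈ 63 unadjusted participants, and r = 0.7 that of 48/0.723² ≈ 92. At r = 0 the interval is about 0.5% to 3% wider, depending on sample size.

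**5. Chance imbalance.** With 24 per arm, the baseline mean difference has a standard deviation of √(2/24) = 0.29 SD. An unadjusted estimate carries r times that amount.

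**6. Which baseline values are safe covariates.** The 17 variables divide as follows:
- 1 has a stated pre-infusion time at visit 2: the adverse effects scale.
- 6 have no stated time but do have a screening value: BDI, HAM-D, STAI, ACQ-NOW, BPRS, PSI.
- 10 have neither: POMS, FTND, craving scale, both SF-12 scales, prose recall, delay discounting, stop signal, digit span, pattern recognition.

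The order of the list in Protocol 7.5 does not settle the timing. The scales come after randomisation and infusion in it, but its first two items, vital signs and bloods, include post-infusion measurements.

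**The case against.** The best defence is that nothing here is an error. Under randomisation, the site-adjusted difference in 6-month means is unbiased and its interval is valid. All inference is labelled exploratory, there are no p-values, and no continuous outcome has a precision target. All of that stands. It limits the point to efficiency, but it is no reason to accept avoidable width.

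A reader might infer more than the documents support:
- *That chance baseline differences bias the results.* They do not. An unadjusted estimate carries only r times the imbalance, and its interval already allows for that variation.
- *That every interval is wider than it need be.* This depends on r, which the documents do not give. Below break-even, adjustment costs a little.
- *That the gain equals the large-sample values of 5%, 13% and 29%, from 1 − √(1 − r²).* These ignore the cost of the extra term.
- *That the visit 2 score can be used as it stands.* For ten variables there is neither a stated pre-infusion time nor a screening value. Adjusting for a score taken after the infusion could remove part of the drug effect.
- *That the relapse result is affected.* The calculation concerns continuous outcomes; it says nothing about the binary primary outcome.

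It is also fair to object that a drinking covariate is undefined as the documents stand. Protocol 7.9.1 leaves the follow-back period unspecified, SAP 5.3 leaves derivation details open, and participants are already abstinent at entry. The value would depend heavily on the window chosen.

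**Conclusion.** The point holds as a loss of precision, not of validity. With 24 versus 24 analysed, adding a pre-infusion baseline value narrows the 95% interval by about 3%, 12% or 28% at assumed correlations of 0.3, 0.5 or 0.7. It widens the interval slightly below about 0.15, or below about 0.2 to 0.25 in the 12 versus 12 comparisons. The size rests on the assumed correlations, a linear model and an equal site split.

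The gain may be small for the adverse effects scale, and for the abstinence outcomes, whose only candidate covariate is earlier drinking. FTND is analysed in smokers only, so its numbers will be smaller and its break-even higher. For ten of the 17 variables, the gain is available only if source records show that the visit 2 value came before the infusion. The change is worth making, but the present plan does not yield invalid results without it.

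**What to change.** Amend SAP 6.3 before unblinding; Protocol 13.6 provides for recorded SAP amendments, and site adjustment itself was added that way. The amendment should state:

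1. Each continuous secondary outcome is analysed by linear regression on arm, site and the pre-infusion baseline value of the same measure.
2. The baseline value is the visit 2 value where source records show it was taken before the infusion. Otherwise it is the screening value, where one exists (BDI, HAM-D, STAI, ACQ-NOW, BPRS, PSI). Otherwise the model adjusts for site only. A post-infusion score is never used.
3. A missing baseline value is replaced by the mean of that measure, so that no participant is dropped for it.
4. Percentage days abstinent and continuous abstinence days are adjusted for site and one drinking measure from the screening timeline follow-back. Its pre-detoxification look-back window and its summary are both fixed in the SAP before unblinding.

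The cost is about a paragraph of text, a check of visit 2 source records for timing, and one degree of freedom per model. No new data are needed. Where the correlation is low there is little gain, and possibly a slightly wider interval. Naming the covariates in advance also closes off a later choice among them.
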